9.2 Subject Accountability

The number of subjects enrolled will be tabulated by country and investigator site overall and by cohort. Subject disposition (including the number enrolled, treated, ended treatment, ended radiographic follow-up and that completed the safety follow-up visit and the study) will be summarized for all enrolled subjects overall and by cohort. Reasons for ending treatment, ending radiographic follow-up and not completing the 30-day safety follow-up visit will be provided overall and by cohort as well.

Key study dates for the first subject enrolled, last subject enrolled, first subject treated, and last subject's end of study will be presented.

9.3 Important Protocol Deviations

Important Protocol Deviations (IPDs) categories are defined by the study team before the first subject's initial visit and updated during the IPD reviews throughout the study prior to database lock. These definitions of IPD categories, subcategory codes, and descriptions will be used during the course of the study. Eligibility deviations are defined in the protocol. Eligibility deviations that are defined as IPDs will be summarized in both the IPD and Eligibility Deviation table and IPD and Eligibility Deviation listings.

9.4 Demographic and Baseline Characteristics

Summary statistics of the following demographic and baseline disease characteristics will be tabulated using the Safety Analysis Set for the following:

- Sex (female, male)
- Age at enrolment (<50, ≥50; < 65, ≥ 65; < 75, ≥ 75 years)
- Region (Europe, Non-Europe)
- PD-L1 status (positive, negative, missing/unknown) at baseline
- Disease stage (stage IVM1a or lower, stage IVM1b/c/d) at baseline
- Disease stage (stage IVM1b or lower, stage IVM1c/d) at baseline

- *BRAF*^{V600} mutation at baseline (yes, no)
- LDH (\leq ULN, $>$ ULN; $\leq 2 \times$ ULN, $> 2 \times$ ULN)
- ECOG PS (0, 1)
- HSV-1 serostatus at baseline (positive, negative, missing/unknown)
- In-transit disease at baseline (yes, no)
- Prior PD-1 therapy (nivolumab, ipilimumab/nivolumab, pembrolizumab, other)
- Prior anti-cancer therapy and line of therapy for current malignancy
- Prior surgery for current malignancy
- Prior radiotherapy for current malignancy

9.5 Efficacy Analyses

Efficacy analysis will be performed on Full Analysis Set (FAS). Primary analysis for the primary efficacy endpoint as well as the key secondary efficacy endpoints will be repeated for the Per Protocol Analysis Set to assess the impact of IPDs. For key efficacy endpoints, sensitivity analyses excluding subjects who received more than one prior line of anti-PD-1 therapy may be performed. The following sections describe analyses of efficacy endpoints.

9.5.1 Analyses of Primary Efficacy Endpoint(s)

Descriptive statistics for the ORR (CR+PR) will be provided where tumor response evaluations are based on investigator assessments using modified RECIST 1.1.

ORR (CR+PR) will be summarized with associated exact 95% confidence intervals (CIs) for binomial proportions ([Clopper & Pearson 1934](#)) (see code fragment in [Appendix B](#)).

[figure not shown]
9.5.2 Analyses of Secondary Efficacy Endpoint(s)

CRR, BOR, DRR and DCR by investigator assessment using modified RECIST 1.1 and iORR, iCRR, iBOR, iDRR and iDCR by investigator assessment using modified irRC-RECIST will be summarized with associated exact 95% CIs for binomial proportions ([Clopper & Pearson 1934](#)) (see code fragment in [Appendix B](#)).

KM estimates and quartiles for DOR, iDOR, PFS, iPFS, OS and Time to subsequent anti-cancer therapy will be provided ([Kaplan and Meier, 1958](#)). KM time to event curves will be presented.

The impact of subsequent anti-cancer therapy on PFS, iPFS and OS will be assessed by censoring at the last evaluable tumor assessment prior to the start of the first subsequent anti-cancer therapy.

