Lesion assessments including radiographic and clinical assessments	X							X					X	Q12W	X	Q12W	Radiographic tumor imaging (CT, PET/CT, or MRI) of the chest, abdomen, and pelvis, and CT or MRI of the brain are required at screening. Tumor assessments must also include all other sites of disease. For subjects who discontinue treatment for any reason other than confirmed iPD per modified irRC-RECIST, every effort should be made to complete radiographic assessments every 12 weeks (±1 week) or more frequently if clinically indicated during the long-term follow-up until documentation of confirmed iPD per modified irRC-RECIST (Section 12.10), clinical progression, start of new anticancer therapy, or end of study, whichever occurs first. Subjects who have reached a confirmed CR may increase their interval of radiographic assessments up to 6 months (26 weeks) after the first 2 years beyond confirmed CR and up to 12 months (52 weeks) after the first 5 years beyond confirmed CR as long as CR is maintained. Radiographic imaging is only required at the safety follow up visit if the subject ended treatment prior to confirmed PD and has not had radiographic tumor imaging performed within 4 weeks (+1 week) of the visit.
Modified RECIST v1.1	X							X					X	Q12W	X	Q12W	Following modified RECIST v1.1 tumor assessments will continue through to PD. See Section 12.10
Modified irRC-RECIST	X							X					X	Q12W	X	Q12W	Following modified irRC-RECIST, tumor assessments will continue until confirmed iPD. See Section 12.10

Footnotes defined on last page of this table

Table 2-1. Schedule of Activities

PROCEDURE	Screening			Treatment Period (Weeks) ^a											Follow-up		Notes
	≤ 28 days	≤ 14 days	≤ 72 hr	0	3	6	9	12	15	18	21	24	>24 ^b	Safety (30 [+7] days post last dose) ^c	Survival ^d		
CLINICAL OUTCOME ASSESSMENTS (CONTINUED)																	
Survival assessment															X	Subjects will be followed for survival every 12 weeks (± 28 days) from the date of the safety follow-up visit (or from the planned visit date if the safety follow-up visit does not occur) until: death, subject withdraws full consent, or up to 36 months after the last subject is enrolled. Assessments will include anticancer therapy, radiation, surgery, disease progression, and serious adverse event reporting as described above and in Sections 9.2.3.1.1.2 and 9.2.3.1.1.3.	

Footnotes defined on last page of this table

Product: Talimogene Laherparepvec (T-VEC)

Protocol Number: 20180115

Date: 09 June 2021

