9.2.2.1 Radiographic Tumor Imaging

Radiographic tumor imaging assessments must include CT scan, PET/CT, or MRI of the abdomen, pelvis, and chest and all other sites of disease. In addition, CT scan or MRI of the brain will be performed at screening and then only if signs or symptoms suggestive of CNS metastasis are present. Imaging will be performed independent of treatment cycle at the time points indicated in the Schedule of Activities (Table 2-1). Imaging should not be adjusted for cycle initiation delays and performed according to the calendar. The imaging modality and image acquisition methods selected (eg, CT or MRI) will remain constant for any individual subject. The radiographic tumor imaging assessments and measurements are performed locally and the response will be assessed by the investigator using modified RECIST v1.1 criteria and modified irRC-RECIST criteria (Section 12.10). However, treatment decisions should be made based on modified irRC-RECIST criteria, NOT based on modified RECIST v1.1 criteria. For subjects who discontinue treatment for any reason other than confirmed iPD per modified irRC-RECIST, every effort should be made to complete radiographic assessments every 12 weeks (± 1 week) or more frequently if clinically indicated during the long-term follow-up until documentation of confirmed iPD per modified irRC-RECIST (Section 12.10), clinical progression, start of new anticancer therapy, or end of study, whichever occurs first. Subjects who have reached a confirmed CR may increase their interval of radiographic assessments up to 6 months (26 weeks) after the first 2 years beyond confirmed CR and up to 12 months (52 weeks) after the first 5 years beyond confirmed CR as long as CR is maintained. Radiographic imaging is only required at the

safety follow-up visit if the subject ended treatment prior to confirmed PD and has not had radiographic tumor imaging performed within 4 weeks (+ 1 week) of the visit.

Radiographic scans taken to confirm disease progression following prior anti-PD-1 therapy may be used for baseline tumor assessments, providing they were performed within 28 days of enrollment.

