Duration of response (DOR) is defined as the time from the date of an initial response of CR or PR to the earlier of PD (see definition of BOR per modified RECIST 1.1) or death. Subjects who have not ended their response at the time of analysis will be censored at their last evaluable tumor assessment date before start of the first subsequent anticancer therapy.

- **Durable response rate (iDRR) per modified irRC-RECIST**

iDRR is defined as the percent of subjects with an iCR or iPR per modified irRC-RECIST with an iDOR \geq 6 months. One month will be calculated based on 365.25 days per year.

- **Durable response rate (DRR) per modified RECIST 1.1**

DRR is defined as the percent of subjects with a CR or PR per modified RECIST 1.1 with a DOR \geq 6 months. One month will be calculated based on 365.25 days per year.

- **End of study (trial) date**

The end of study date is defined as the date when the last subject across all sites is assessed or receives an intervention for evaluation in the study (i.e., last subject last visit), following any additional parts in the study (e.g., long-term follow-up), as applicable.

- **Evaluable tumor assessment**

An overall visit response other than unevaluable (UE or iUE).

- **Events of clinical interest pembrolizumab**

Selected non-serious and serious adverse events known as pembrolizumab events of clinical interest (ECI) that occur after the first dose of pembrolizumab through 90 (+7) days after the last dose of pembrolizumab, or 30 (+7) days after initiation of a new anticancer therapy, whichever is earlier must be reported to Amgen within 24 hours.

- **Events of interest (EOI) for talimogene laherparepvec**

EOIs for talimogene laherparepvec are defined in the version-controlled EOI search strategies maintained by Global Regulatory Affairs and Safety (GRAAS) at Amgen for talimogene laherparepvec

[figure not shown]
- **Investigational product (IP)**

[figure not shown]
Investigational product (IP) refers to Amgen IP talimogene laherparepvec and non-Amgen IP pembrolizumab in this study. IP is also referred as study drug or study therapy.

- **Last date known to be alive**

For subjects not known to have died, their last date known to be alive will be determined as the latest date associated with clinic visits before data cutoff date including, for example, but not limited to the following:

1. Survival status: Last subject status date if status of subject is "Alive"

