2. End of study date if the subject's primary reason for ending study is not "Lost to follow-up"
3. Any subsequent anti-tumor therapy initialization date
4. AE start or end date
5. Procedure and concomitant medication start/end date
6. Date of lesion assessments
7. Date of herpetic lesion swabbing
8. Visit date of vital signs; physical exam; ECOG; sample collection for local lab and central lab parameters including HSV-1
9. Date of last investigational product administration

- Objective response rate (ORR) per modified RECIST 1.1

ORR is defined as the incidence of a BOR of CR or PR per modified RECIST 1.1. Subjects who do not have any post-baseline tumor assessments will be regarded as non-responders.

- **Objective response rate (iORR) per modified irRC-RECIST**

iORR is defined as the incidence of an iBOR of iCR or iPR per modified irRC-RECIST. Subjects who do not have any post-baseline tumor assessments will be regarded as non-responders.

- **Overall survival (OS)**

Overall survival is defined as the interval from first dose to death from any cause. Subjects without an event will be censored at the last date known to be alive.

- **PD-L1 Status**

PD-L1 expression from tumor biopsy tissue samples will be reported as positive or negative. PD-L1 expression is said to have positive status if the **combined positive score (CPS)** is $\geq 1\%$, and negative status if **CPS** is $<1\%$.

- **Primary completion date**

The primary completion date is defined as the date when the last subject is assessed or receives an intervention for the final collection of data for the primary endpoints for the purpose of conducting the primary analysis, whether the study concluded as planned in the protocol or was terminated early.

The primary completion date is the date when the last subject has completed the assessments for week 24.

- **Progression-free survival (iPFS) per modified irRC-RECIST**

iPFS per modified irRC-RECIST is defined as the interval from first dose to the earlier event of iPD (per modified irRC-RECIST) or death from any cause. Subjects without an event will be censored at their last evaluable post-baseline tumor assessment if available, otherwise will be censored on study day 1.

- **Progression-free survival (PFS) per modified RECIST 1.1**

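### The check of later therapy on OS censors at the last tumour scan, which discards known-alive time and can only lower the curve relative to censoring at therapy start

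*SAP*

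**What the plan says.** SAP 9.5.2 sets one rule for three endpoints. It names them as "The impact of subsequent anti-cancer therapy on PFS, iPFS and OS", to be examined by a version that "will be assessed by censoring at the last evaluable tumor assessment prior to the start of the first subsequent anti-cancer therapy".

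SAP section 5 treats OS differently in the main analysis. "Overall survival is defined as the interval from first dose to death from any cause", so no tumour assessment enters the definition. "Subjects without an event will be censored at the last date known to be alive", and the list of dates that establish this includes "Any subsequent anti-tumor therapy initialization date". An assessment counts as evaluable only if the visit response was not unevaluable under either set of criteria.

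On timing, Protocol Table 2-1 places the first on-study scan at week 12. For subjects who stop treatment without confirmed iPD, "every effort should be made to complete radiographic assessments every 12 weeks", ending at confirmed iPD, "clinical progression, start of new anticancer therapy, or end of study, whichever occurs first" (Protocol 9.2.2.1). For other subjects, assessment under modified irRC-RECIST runs until confirmed iPD (Protocol 9.2.2.3). Survival contact continues separately (Protocol 9.1.4).

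**The concern.** After the last scan, progression status is unknown, so the scan date is a natural censoring point for PFS and iPFS. Survival status is not unknown: a subject who begins another therapy was alive that day, and the SAP says so itself.

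Under the rule, whether a subject is at risk between the last scan and new therapy depends on what happens later. Those who survive to start therapy are withdrawn from that interval. Those who die in it without starting therapy stay and are counted as deaths. Survivors are removed selectively, so the death rate in the interval is overstated relative to censoring at therapy start.

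At stake is the reading of this check. It is the only analysis visible in the public text that addresses later therapy and OS, and it is read by comparing it with the main OS curve. Anything the rule adds enters that comparison directly.

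**Working it through.** **No plan figure to reproduce.** The documents give no OS median, event target, switching rate or scan-to-therapy gap.

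**Direction relative to censoring at therapy start.** The Kaplan-Meier estimate is S(t) = Π(1 − d_j/n_j) over death times up to t. Deaths after new therapy are excluded under either date, so every d_j is the same. The scan date is never later than the therapy start, so every n_j is equal or smaller. Each factor, and so S(t), is equal or smaller. This needs no assumption about the data.

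**Ten-subject illustration.** Five subjects die at weeks 20, 30, 44, 60 and 100. Five others start therapy at weeks 23, 34, 47, 70 and 90, with last scans at weeks 12, 24, 36, 60 and 84.

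- Censored at start, the risk sets at weeks 20, 30, 44 and 60 are 10, 8, 6 and 4. S(44) = 9/10 × 7/8 × 5/6 = 0.656; S(60) = 0.656 × 3/4 = 0.492.
- Censored at last scan, they are 9, 7, 5 and 4. S(44) = 8/9 × 6/7 × 4/5 = 0.610; S(60) = 0.610 × 3/4 = 0.457.

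**Size, and net direction.** Simulation, 400,000 subjects per row. From the documents: 12-weekly scans, and a confirming scan at least 4 weeks after first iPD. Assumed: median time to progression 20 weeks; median OS 120 weeks at the pre-progression hazard; death hazard multiplied by 1, 2 or 4 after progression; 70% of progressors eligible for new therapy; last scan taken as the confirming scan; exponential gap to therapy; no effect of new therapy; cut-off at 156 weeks. Between 37 and 56% switch. OS at 52 weeks, in %:

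| Hazard after progression | Mean gap (weeks) | Truth | Censored at start | Censored at last scan | Scan − start | Scan − truth |
|---|---|---|---|---|---|---|
| ×1 | 2.0 | 74.0 | 74.0 | 73.3 | −0.7 | −0.7 |
| ×1 | 5.8 | 74.0 | 74.0 | 72.1 | −1.9 | −1.9 |
| ×1 | 11.2 | 74.0 | 74.0 | 70.7 | −3.3 | −3.3 |
| ×2 | 2.0 | 63.3 | 65.5 | 64.7 | −0.8 | +1.4 |
| ×2 | 5.6 | 63.3 | 65.0 | 62.8 | −2.2 | −0.5 |
| ×2 | 10.6 | 63.4 | 64.5 | 60.8 | −3.7 | −2.6 |
| ×4 | 1.9 | 47.9 | 52.8 | 51.9 | −0.9 | +4.0 |
| ×4 | 5.3 | 47.9 | 51.6 | 49.2 | −2.4 | +1.3 |
| ×4 | 9.4 | 48.0 | 50.6 | 47.0 | −3.6 | −1.0 |

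The scan-minus-start column is always negative and depends mainly on the gap. The scan-minus-truth column changes sign.

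A second set of runs takes the last scan as the one that first shows progression, with OS independent of progression, true median OS 78 or 104 weeks and 37 to 48% switching. A median gap of 4 weeks lowers 52-week OS by 2.3 points (63.0 − 60.7) or 2.0 points (70.6 − 68.6). A median gap of 12 weeks lowers it by 5.1 points (63.1 − 58.0) or 4.5 points (70.7 − 66.2).

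**Missing date.** PFS and iPFS fall back to study day 1 when there is no evaluable post-baseline assessment (SAP section 5). SAP 9.5.2 gives no such fallback for OS. A subject who switches before the week 12 scan therefore has no defined OS censoring date in this check.

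**The case against.** The strongest reply is that the net direction is not established. A reader might infer that this OS curve is biased downward, that censoring at therapy start would recover the true OS, and that the check would mislead people into thinking later therapy had raised the main OS estimate. Those statements hold if progression does not change the risk of death, which is implausible in metastatic melanoma. If progression raises that risk, removing progressed subjects at new therapy pushes the curve up. With true 12-month OS of 63% and a 4-week median gap, last-scan against therapy-start censoring gave 60.5% and 62.9% with no extra hazard, 62.4% and 64.6% at twice the hazard, and 63.5% and 65.7% at four times. In the last two cases the planned rule lies nearer the truth. This stands: the documents do not support a claim about net direction.

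The gap may also be short. Confirming scans count as evaluable, a scan is required at the safety visit if treatment ended before confirmed progression without recent imaging, and subjects who leave treatment without confirmed iPD go on being scanned. This stands too, and it is why the range starts near 1 point. It does not remove the effect.

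Finally, the shift is smaller than sampling error. At 63% with 72 subjects and no censoring, the standard error is √(0.63 × 0.37/72) = 5.7 points. But the check and the main analysis use the same subjects, so the shift does not behave like independent noise in their contrast. Nor does an accidental offset of unknown size justify the rule, because the two effects cannot be separated in the output.

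**Conclusion.** The point holds as a comparison between two censoring dates. For OS, the scan-date rule discards known-alive time selectively and gives a curve equal to or below the one censored at therapy start. That direction is certain. The size, about 1 to 5 points in 12-month OS, rests on the assumed gaps, switching rates and hazards above. The position of either curve relative to OS without later therapy cannot be settled from the documents, since both carry informative censoring.

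The consequence is limited. This is a supportive check of a secondary endpoint in a trial without hypothesis testing. The main OS analysis, which censors at the last known-alive date, and the primary ORR do not change. The correction is still worth making, because the rule lets a future event decide who is at risk and leaves early switchers without a date.

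**What to change.** In SAP 9.5.2, confine the last-evaluable-assessment rule to PFS and iPFS. For the OS check, state that subjects who start subsequent anti-cancer therapy are censored on the start date of the first such therapy, and that all others are handled as in the main OS analysis. This also supplies a date for anyone who switches before an evaluable post-baseline scan.

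Label the result supportive and add a sentence that censoring at new therapy remains informative if switching is related to prognosis. Inverse-probability-of-censoring weighting is an option, but 72 subjects leave little room for it.

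The cost is a short SAP edit and one changed censoring variable. The therapy start date is already collected and is needed for time to subsequent anticancer therapy.

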9.5.3 Analyses of Exploratory Efficacy Endpoint(s)

9.6 Safety Analyses

9.6.1 Adverse Events

Safety analyses will be conducted separately for each cohort on Safety Analysis Set (SAS). The Medical Dictionary for Regulatory Activities (MedDRA) version 21.1 or later will be used to code all adverse events (AE). The CTCAE version 5.0 or later will be used to grade severity of adverse events.

The subject incidence of AEs will be summarized for all treatment-emergent AEs, serious AEs, AEs leading to withdrawal of investigational product, grade 3 or 4 AEs, fatal AEs, events of interests (EOIs) for talimogene laherparepvec and pembrolizumab events of clinical interest (ECI). Subject incidence of EOI/ECIs will be summarized by the EOI/ECI categories. Preferred terms within each EOI/ECI category will also be summarized.

The subject incidence of all treatment-related AEs, serious AEs, AEs leading to withdrawal of investigational product, grade ≥ 3 AEs, fatal AEs, and EOs for talimogene laherparepvec will be tabulated by system organ class and preferred term in descending order of frequency.

Summaries of treatment-emergent and serious AEs occurring in at least 5% of the subjects by preferred term will be provided in descending order of frequency.

A Listing will be provided for treatment-emergent adverse events and treatment-emergent serious adverse events. In addition, death on study will be listed.

Potential or known unintended exposure to talimogene laherparepvec, related suspected signs or symptoms, and detection of talimogene laherparepvec in a subject's household member, caregiver, or healthcare provider will be summarized.

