Safety analyses will be performed on the Safety Analysis Set (SAS) defined as all enrolled subjects who received at least 1 dose of talimogene laherparepvec or pembrolizumab. Summaries of the incidence of treatment-emergent and

treatment-related adverse events (all adverse events, grade ≥ 3 adverse events, serious adverse events, fatal adverse events, adverse events defined as events of interest) will be provided. Incidence of all grade 3 and higher laboratory toxicities will be reported. Descriptive statistics will be provided for laboratory test results and biomarker endpoints as appropriate.

[figure not shown]
For a full description of statistical analysis methods, please refer to Section [10](#).

Sponsor Name: Amgen Inc.

2. Study Schema and Schedule of Activities

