4.1 Objectives and Endpoints

Objectives	Endpoints
Primary	

 • To evaluate the efficacy of talimogene laherparepvec in combination with pembrolizumab as assessed by objective response rate (ORR) in subjects with unresectable/metastatic stage IIIB-IVM1d melanoma who have progressed on prior anti-PD-1 therapy 	
 • Overall response (complete response [CR] + partial response [PR]) (by investigator assessment using modified RECIST v1.1)
Key Secondary	

 • To evaluate the efficacy of talimogene laherparepvec in combination with pembrolizumab, as assessed by: 
 ○ Complete response rate (CRR), best overall response (BOR), durable response rate (DRR), duration of response (DOR), and disease control rate (DCR) ○ ORR using modified irRC-RECIST ○ Progression free survival (PFS) ○ Overall Survival (OS) 	
 • Complete response, BOR, durable response, DOR, and disease control, (investigator assessment using modified RECIST v1.1 and modified irRC-RECIST) and overall response using modified irRC-RECIST by investigator assessment • PFS (by investigator assessment using modified RECIST v1.1 and modified irRC-RECIST) • OS

 • To evaluate the safety of talimogene laherparepvec in combination with pembrolizumab as assessed by incidence of treatment-emergent and treatment-related adverse events, and abnormal laboratory tests in patients who have progressed on prior anti-PD-1 therapy 	
 • Incidence of treatment-emergent and treatment-related adverse events (all adverse events, grade \geq 3 adverse events, serious adverse events, fatal adverse events, adverse events defined as events of interest), and abnormal laboratory tests

 • To evaluate time to subsequent anticancer therapy 	
 • Time to subsequent anticancer therapy

	Exploratory

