2.1 Objectives and Endpoints

Objectives	Endpoints
Primary	

 • To evaluate the efficacy of talimogene laherparepvec in combination with pembrolizumab as assessed by objective response rate (ORR) in subjects with unresectable/metastatic stage IIIB-IVM1d melanoma who have progressed on prior anti-PD-1 therapy 	
 • Overall response (complete response [CR]+partial response [PR]) (by investigator assessment using modified RECIST v1.1)
Key Secondary	

 • To evaluate the efficacy of talimogene laherparepvec in combination with pembrolizumab, as assessed by: 
 ○ Complete response rate (CRR), best overall response (BOR), durable response rate (DRR), duration of response (DOR), and disease control rate (DCR) ○ ORR using modified irRC-RECIST ○ Progression free survival (PFS) ○ Overall survival (OS) 	
 • Complete response, BOR, durable response, DOR and disease control, (investigator assessment using modified RECIST 1.1 and modified irRC-RECIST) and overall response using modified irRC-RECIST by investigator assessment • PFS (by investigator assessment using modified RECIST 1.1 and modified irRC-RECIST) • OS

 • To evaluate the safety of talimogene laherparepvec in combination with pembrolizumab as assessed by incidence of treatment-emergent and treatment-related adverse events, and abnormal laboratory tests in patients who have progressed on prior anti-PD-1 therapy 	
 • Incidence of treatment-emergent and treatment-related adverse events (all adverse events, grade ≥ 3 adverse events, serious adverse events, fatal adverse events, adverse events defined as events of interest), and abnormal laboratory tests

• To evaluate time to subsequent anticancer therapy	
• Time to subsequent anticancer therapy
---	---

Exploratory	
	

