8.3 Handling of Missing and Incomplete Data

Every effort will be made to obtain complete data in the clinical study. Partial or missing dates of adverse events and concomitant medications will be imputed. Adverse events with missing IP relatedness, seriousness, or CTCAE severity grades are included in TEAE as long as the events qualify for the reporting period. Events with missing relatedness, seriousness, and severity grades will be excluded from treatment-related, serious, and with a CTCAE grade of 3 or higher AE analysis, respectively. [REDACTED]

[REDACTED]

[REDACTED]

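### SAP 9.6.1 summarises treatment-emergent AEs as grade 3 or 4 plus a separate fatal row, while the stated secondary endpoint is grade ≥ 3 for both treatment-emergent and treatment-related AEs

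*SAP*

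**What the plan says.** **Endpoint.** Protocol 4.1 opens the secondary safety endpoint with "Incidence of treatment-emergent and treatment-related adverse events (all adverse events, grade" and sets the threshold at grade ≥ 3. SAP 2.1 repeats it, listing "grade ≥ 3 adverse events, serious adverse events, fatal adverse events". The protocol synopsis commits to the same summaries under its statistical considerations: "treatment-related adverse events (all adverse events, grade ≥ 3 adverse events, serious adverse events".

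**Planned tables.** SAP 9.6.1 has two sentences on AE incidence. The one for treatment-emergent AEs includes "AEs leading to withdrawal of investigational product, grade 3 or 4 AEs, fatal AEs". The one for treatment-related AEs reads "The subject incidence of all treatment-related AEs, serious AEs, AEs leading to withdrawal of investigational product, grade ≥ 3 AEs", followed by fatal AEs and talimogene events of interest. The section says that safety is analysed by cohort. SAP 9.1 adds pooled analyses.

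**Elsewhere in the SAP.** The missing-data rule in SAP 8.3 leaves events without a grade out of the analysis it describes as "with a CTCAE grade of 3 or higher AE analysis". SAP 10, on changes from the protocol-specified analyses, says there are none.

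**Windows.** In SAP 5, a treatment-emergent AE runs to 30 days after the last dose. A treatment-emergent serious AE runs to 90 days, or to 30 days if new anticancer therapy starts.

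**The concern.** Grade ≥ 3 covers grades 3, 4 and 5. A grade 3–4 row with a separate fatal row covers the same grades but splits the endpoint category in two. Subject incidences in two rows cannot simply be added, because one person may have a grade 3 or 4 event and also a fatal one.

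An analyst who follows 9.6.1 literally would not tabulate the treatment-emergent grade ≥ 3 category that the endpoint names. The treatment-emergent figure would also rest on a different definition from the treatment-related one beside it. With cohorts of 15 and 27, a single subject shifts the percentage visibly.

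**Working it through.** **1. Endpoint against tables**

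| Category needed | Endpoint (Protocol 4.1, SAP 2.1) | SAP 9.6.1 |
|---|---|---|
| Treatment-emergent | grade ≥ 3 | grade 3 or 4, with fatal as a separate row |
| Treatment-related | grade ≥ 3 | grade ≥ 3 |

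The second row assumes that the word treatment-related governs the whole of the second sentence. If it governs only the first item, the treatment-related grade ≥ 3 row is not assured. On either reading, 9.6.1 names one grade ≥ 3 row where the endpoint needs two.

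**2. Can the missing figure be recovered from the two rows?**

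Let m be the subjects in the grade 3–4 row, f those in the fatal row, b those in both, and N the group size. In a common window:

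- subjects with grade ≥ 3 = m + f − b
- b lies between 0 and min(m,f)
- so the incidence lies between max(m,f)/N and (m+f)/N, a width of min(m,f)/N.

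If each subject is counted once at worst grade, b = 0 and the sum is exact. SAP 9.6.1 does not state that rule. Protocol 12.4 has sites record a separate event for each rise in severity, so one subject can hold both a grade 3–4 and a fatal record. That instruction governs the CRF and does not settle how the table counts.

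**3. Are the windows the same?**

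The fatal row has no stated window. Under Protocol 12.4 every fatal event is serious, so either the 30-day or the 90-day definition could be applied. If the fatal row runs longer than the grade 3–4 row, even worst-grade counting does not make the sum a 30-day incidence.

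**4. Size, with assumed counts**

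The documents give no counts for this trial. Those below are assumptions; N = 72, 27 and 15 are the enrolled numbers in Protocol 5.2.

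| N | m | f | Lower bound | Upper bound | Width |
|---|---|---|---|---|---|
| 72 | 20 | 2 | 20/72 = 27.8% | 22/72 = 30.6% | 2/72 = 2.8 points |
| 72 | 20 | 4 | 20/72 = 27.8% | 24/72 = 33.3% | 4/72 = 5.6 points |
| 27 | 8 | 2 | 8/27 = 29.6% | 10/27 = 37.0% | 2/27 = 7.4 points |
| 15 | 4 | 1 | 4/15 = 26.7% | 5/15 = 33.3% | 1/15 = 6.7 points |

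The values f = 2 and f = 4 for N = 72 are of the order suggested by the ipilimumab combination studies in Protocol 3.2.2: 3 of 93 gives 72 × 3/93 = 2.3, and 1 of 18 gives 72 × 1/18 = 4.0. Those are other populations and another partner drug. They show only that f may well exceed zero and say nothing about the overlap b.

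**The case against.** The strongest reply is that this is a label, not a lost analysis. SAP 2.1 keeps grade ≥ 3 as the endpoint, SAP 8.3 presupposes that analysis, and the synopsis commits to it, so a programmer may well produce the row anyway. Treatment-emergent AEs are also to be listed, so a count could be checked if the listing shows grade. With ordinary worst-grade counting the two rows add exactly. The study is descriptive, pooled safety figures are planned alongside the cohort ones, and Protocol 10.4.2.3.1 names no grade table.

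Most of this stands and limits the consequence. It does not remove the mismatch: 9.6.1 is the section that specifies the tables, and it conflicts with the endpoint and with 8.3. The silence of Protocol 10.4.2.3.1 does not override the endpoint in 4.1 or the synopsis.

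Three stronger readings are tempting, and the documents do not support them:

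- **That grade 5 events drop out.** They do not; fatal AEs have their own row in both sentences.
- **That grade ≥ 3 incidence can never be derived.** This goes too far, because the counting rule is unstated rather than wrong.
- **That late talimogene-related events go unreported.** Protocol 9.2.3.1.1 records them to the end of long-term follow-up, and the SAP listings cover only treatment-emergent AEs, treatment-emergent serious AEs and deaths. But the table of all treatment-related AEs has no stated window and can include them, and Protocol 10.4.2.3.1 asks for tables, not listings. A further listing would be a reporting preference.

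**Conclusion.** The mismatch is real on the current text. For treatment-emergent AEs, SAP 9.6.1 does not name the grade ≥ 3 category that the secondary endpoint requires, and SAP 10 records no change. The consequence is modest: every fatal event is still reported and no decision rule depends on the row. What is at risk is a clear figure for one stated endpoint category.

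If the rows overlap, the ambiguity is at most min(m,f)/N, which is 2.8 to 7.4 points in the assumed examples. It is zero if each subject is counted once at worst grade in a common window. The example widths rest on assumed counts and are not forecasts.

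**What to change.** In SAP 9.6.1:

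1. For treatment-emergent AEs, replace the grade 3 or 4 category with grade ≥ 3, covering grades 3 to 5, with each subject counted once, in the treatment-emergent AE window of SAP 5. A grade 3–4 row may stay as an extra.
2. In the second sentence, write treatment-related grade ≥ 3 explicitly.
3. State the window for fatal AEs.

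Optionally, state whether the treatment-related table includes talimogene-related events with onset after the treatment-emergent AE and serious AE windows. This is a clarification and not part of the error.

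The cost is a few words and one table row from data already on the CRF. The one drawback is that the reported treatment-emergent figure may be slightly higher than a grade 3–4 figure, because it includes subjects whose only qualifying event was fatal.
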